### **3.8.3 Overall Survival**

Overall survival (OS) time will be based on data collected during study and Post Study Follow-up. OS time is defined as the time from the start date of the treatment (Day 1) to the date of death due to any cause and will be analyzed descriptively.

The number and percentage of subjects who died, who were lost to follow up, and who survived will be summarized. Subjects who withdrew from the study or were lost to follow-up (survival status unknown) will be censored at the date of last contact/last data point collected in the CRF.

OS Rate and the corresponding 95% confidence intervals at 6 months and 12 months will be calculated based on Kaplan-Meier product limit estimates and will be displayed along with the corresponding number of subjects at risk at each time point. OS time will be summarized descriptively. The 25th percentile, median, 75th percentile, corresponding 95% CIs as well as the minimum and maximum survival time will be calculated using the Kaplan-Meier method. In addition, OS estimates will be presented graphically.

## **3.9 Safety Analysis**

All safety analyses will be performed using the ITT population. For clinical laboratory, data collected from all core study cycles and/or on-study follow-up assessments will be analyzed for each subject. For vital signs, ECOG performance status, and ECG, only data collected from the first two cycles and/or on-study follow-up assessments will be analyzed for each subject. All subject data including those from the additional cycles will be presented in subject listings.

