#### **3.1.2 Reporting of Numerical Values**

All clinical study data will be presented in subject data listings. All by-visit summarizations will be conducted using data from Cycle 1, Cycle 2, and/or the last cycle, as applicable. All data presentations will be by the planned cohorts in the protocol, separately for Phase 1 and Phase 2.

Descriptive statistics (n, mean, standard deviation, median, minimum and maximum) will be calculated by cohort for continuous variables.

Frequencies and percentages will be presented by cohort for categorical and ordinal variables. If there are missing values, the number missing will be presented, but without a percentage.

Means and medians will be reported to one decimal place more than the data reported in the EDC. Standard deviations will be reported to two decimal places more than the data reported. Minimum and maximum will be reported to the same number of decimal places captured in the EDC.

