### 3.3.2 Safety Variables

Safety variables include:

- Incidence of treatment emergent adverse events (TEAEs), defined as an adverse event (AE) that is first identified, or is identified to worsen in intensity, at a time point occurring after the first dose of study drug
  - All TEAEs by System Organ Class (SOC) and Preferred Term (PT)
  - All TEAEs by PT
  - TEAEs by maximum severity (according to CTCAE version 4.03)
  - Treatment related TEAEs (TRAЕ) defined as events with a relationship to any study drug of ‘Definitely Related’, ‘Probably Related’ or ‘Possibly Related’
  - Treatment related TEAEs by maximum severity (according to CTCAE version 4.03)
  - TEAEs leading to study drug withdrawal
  - Serious TEAEs
- Change in clinical laboratory parameters (hematology, chemistry, amylase, lipase, thyroid) from baseline to each selected post-treatment assessment time point and shifts in clinical laboratory parameters from baseline to each selected post-treatment assessment time point
- Change in vital signs (systolic and diastolic blood pressure, heart rate, respiratory rate, and body temperature) from pre-dose to end of infusion at selected post-treatment assessment time points
- Change in ECOG performance status from baseline to last assessment
- Shifts in ECG from baseline to each selected post-treatment assessment time point

- Shifts in ECHO or MUGA from baseline to each selected post-treatment assessment time point

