### **3.9.4 ECOG Performance Status**

ECOG Performance Status will be summarized by cohort by presenting the number and percentage of subjects with ECOG score 0, 1, 2, 3, and 4 at baseline and ECOG score of 0, 1, 2, 3, 4, and 5 at the last on-treatment assessment time point (including optional treatment extension time points) and last on-study follow-up time point for which ECOG Performance Status was assessed. ECOG data will be provided in a subject listing.

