### **3.9.5 12-Lead ECG**

Shift of normality status (normal, abnormal with no clinical significance, abnormal with clinical significance) from baseline to each selected post-treatment assessment time point will be presented for the ECG data. Based on the number of subjects who had non-missing results for both baseline and corresponding post-treatment assessment time point, percentages for the shift tables will be calculated. ECG results will be provided in a subject listing.

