Table 14.3.6.4	Incidence of Pegylated Liposomal Doxorubicin (PLD) Related Adverse Events By Maximum CTCAE Grade, MedDRA System Organ Class and Preferred Term, ITT Population
Table 14.3.7.1	Incidence of Treatment Related Adverse Events Leading to MEDI4736 Withdrawal by MedDRA System Organ Class and Preferred Term, ITT Population
Table 14.3.7.2	Incidence of Treatment Related Adverse Events Leading to Motolimod Withdrawal by MedDRA System Organ Class and Preferred Term, ITT Population
Table 14.3.7.3	Incidence of Treatment Related Adverse Events Leading to PLD Withdrawal by MedDRA System Organ Class and Preferred Term, ITT Population
Table 14.3.8	Incidence of Serious Adverse Events by MedDRA System Organ Class and Preferred Term, ITT Population
Table 14.4.1	Hematology Parameters – Change from Baseline, ITT Population
Table 14.4.2	Hematology Parameters – Shift from Baseline, ITT Population
Table 14.4.3	Chemistry Parameters – Change from Baseline, ITT Population
Table 14.4.4	Chemistry Parameters – Shift from Baseline, ITT Population
Table 14.4.5	Vital Signs – Change from Pre-dose to End of Infusion, ITT Population

Table 14.4.6	ECOG Performance Status at Baseline and Last Assessment, ITT Population
Table 14.4.7	ECG-Shift from Baseline, ITT Population
Table 14.4.8	ECHO or MUGA-Shift from Baseline, ITT Population

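### SAP 3.9 and 3.9.4 set incompatible windows for on-treatment ECOG data after Cycle 2, and Table 14.4.6 as described does not show the within-subject change declared in 3.3.2

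*SAP*

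**What the plan says.** Four places in the SAP bear on which ECOG values are summarised.

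- The preamble to the safety analysis (3.9) covers vital signs and two further measures: "ECOG performance status, and ECG, only data collected from the first two cycles and/or on-study follow-up assessments will be analyzed".
- The ECOG section (3.9.4) reports scores at baseline and then "at the last on-treatment assessment time point (including optional treatment extension time points) and last on-study follow-up time point".
- The list of safety variables (3.3.2) names "Change in ECOG performance status from baseline to last assessment", and the only ECOG table, 14.4.6, is titled "ECOG Performance Status at Baseline and Last Assessment, ITT Population".
- The general reporting rule (3.1.2) says "All by-visit summarizations will be conducted using data from Cycle 1, Cycle 2, and/or the last cycle, as applicable". This admits a last cycle, which 3.9 does not do for ECOG.

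On the form of the output, 3.9.4 describes "presenting the number and percentage of subjects with ECOG score 0, 1, 2, 3, and 4 at baseline and ECOG score", followed by the same kind of count at the later time points. For ECG, by contrast, 3.9.5 plans a shift in status "from baseline to each selected post-treatment assessment time point will be presented for the ECG data". ECHO/MUGA (3.9.6) is handled in the same way. Both of those sections base percentages on subjects with baseline and post-treatment values; 3.9.4 states no such rule.

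**The concern.** There are two separate problems.

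The first is the data window. SAP 3.9 names ECOG and uses the word only; 3.9.4 asks for the last on-treatment value and extends it into the optional treatment period. The SAP has no rule on which section takes precedence. Two programmers could each follow the SAP and produce different on-treatment columns in Table 14.4.6.

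The second is the form of the table. SAP 3.1.3 defines change from baseline subject by subject, and 3.3.2 declares ECOG change as a safety variable. Counts per score at separate time points are marginal distributions and do not determine how individual subjects moved. At stake is whether the summary table reports, for each subject, how performance status at the end of treatment compares with entry. No hypothesis test depends on it.

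**Working it through.** The plan gives no figure to reproduce here. The check is a count of scheduled visits, followed by bounds on what marginal counts can show.

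**Schedule.** In the protocol flowchart (3.2), ECOG is recorded with the physical examination at screening, on Day 1 of Cycles 1 to 12, and at each of the three on-study follow-up visits. In the extension (protocol 8.9.1) it is recorded every 4 weeks. Day 1 of Cycle k falls on study day 1 + 28(k − 1):

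- Cycle 2: 1 + 28 = Day 29
- Cycle 12: 1 + 28 × 11 = Day 309

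**Window.** Take Cycle 1 Day 1 as pre-dose, hence baseline. This is an inference, because the flowchart does not attach its pre-dose footnote to that row. The post-baseline core assessments are then Cycles 2 to 12, which is 11.

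| Rule | Latest on-treatment ECOG, 12-cycle subject | Post-baseline core assessments eligible | Follow-up score used |
|---|---|---|---|
| SAP 3.9 | Day 29 | 1 of 11 | yes |
| SAP 3.9.4 | Day 309, or an extension visit | any of 11; the last is used | yes |

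The Day 29 ceiling holds whether or not Cycle 1 Day 1 was pre-dose. Both rules keep follow-up, so the conflict is confined to on-treatment scores after Cycle 2.

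**Form of the table.** The documents give no baseline ECOG distribution, so the splits below are assumptions. N = 41 is the planned number of evaluable Phase 2 subjects (SAP 2.2.1). All subjects are taken to have both values.

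*Identical margins at both times, scores 0 and 1 only.* If x subjects move from 0 to 1, then x must move from 1 to 0, so 0 ≤ x ≤ min(n0, n1).

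| Baseline ECOG 0 / 1 | Possible number who worsened | Upper end as share of 41 |
|---|---|---|
| 10 / 31 | 0 to 10 | 24% |
| 20 / 21 | 0 to 20 | 49% |
| 30 / 11 | 0 to 11 | 27% |

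*Some last scores of 2.* Take baseline 20 / 21 at ECOG 0 / 1 and last scores 20 / 15 / 6 at ECOG 0 / 1 / 2. The 6 at score 2 have all worsened, because entry requires 0 or 1 (protocol 5.1, criterion 5). The number who worsened is therefore 6 + x, where x is the number moving from 0 to 1.

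- Minimum x = 0: all 20 at score 0 stay there, and of the 21 at score 1, 15 stay and 6 move to 2. Total 6.
- Maximum x = 15: everyone whose last score is 1 started at 0. Total 6 + 15 = 21.

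The same table is compatible with anything from 6 to 21 subjects worsening. The 6 at score 2 are visible, but not whether each fell by one grade or two.

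**The case against.** The strongest reply is that the intended rule is fairly clear. SAP 3.9 is a general preamble; 3.9.4 is specific to ECOG and deliberately mentions the extension; 3.3.2 and the table title agree with it. The two-cycle wording looks like a leftover. That reading is probably right, and the fix adopts it. It does not remove the contradiction, because 3.9 names ECOG expressly.

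A reader might go further and infer that 3.9 confines ECOG to two cycles and that decline can be hidden. The documents do not support that. SAP 3.9 keeps on-study follow-up and 3.9.4 tabulates the last follow-up score, so a decline that persists would appear. Under 3.9.4 any last score of 2 or more in an eligible subject shows directly. Listing 16.2.26 carries the ECOG data, and 3.9 says data from additional cycles are listed too. Clinically significant deteriorations are also to be recorded as adverse events (protocol 4.2.1), and the TEAE summaries carry no two-cycle limit.

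A reader might also cite the performance-status criterion in protocol 3.1.10.1. That is an investigator's decision about an individual subject during treatment and does not depend on an end-of-study table.

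Two further replies have some force. The bounds above are mathematical extremes: 20 of 41 worsening with unchanged margins needs every ECOG 0 subject to worsen and 20 of the 21 ECOG 1 subjects to improve. And protocol 4.2.2 names no ECOG summary, so a shift table is not a protocol requirement. It follows from the SAP's own declaration of change in 3.3.2. The table shells are not in the documents, so the marginal form is read from 3.9.4 and the title.

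**Conclusion.** Both parts hold, and both are minor.

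For subjects treated beyond Cycle 2, the on-treatment rules in SAP 3.9 and 3.9.4 exclude each other. Under 3.9, 10 of the 11 post-baseline core assessments and all extension assessments fall outside the analysis, and a later on-treatment decline enters the table only if it is still present at the last on-study follow-up. This is a count of scheduled visits, not an estimate of lost information.

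Under either rule, the counts in 3.9.4 do not deliver the change declared in 3.3.2. Last scores of 2 or more identify subjects who worsened, but the total is not identifiable: declines from 0 to 1 can be offset by improvements from 1 to 0, and a score of 2 does not show its starting value. The numerical ranges rest on assumed splits and illustrate the point only.

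The subject-level data are kept in full, and the primary analysis, the populations and the sample size are unaffected.

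**What to change.** 1. In SAP 3.9, take ECOG performance status out of the sentence that limits analysis to two cycles plus follow-up, so that 3.9.4 governs.
2. In SAP 3.9.4, make Table 14.4.6 a shift table of baseline by last on-treatment ECOG (extension included) and baseline by last on-study follow-up ECOG. Base percentages on subjects with both values, as 3.9.5 and 3.9.6 already do, and retitle the table to match.

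The cost is one deleted phrase and one reshaped table; the data are already collected. Because the table would still use the last score rather than the worst, a temporary decline would remain visible only in the listing.

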### **3.9.1 Adverse Events**

All adverse events will be coded using the Medical Dictionary of Regulatory Activities (MedDRA) Version 19.0 and will be classified by MedDRA system organ class (SOC) and preferred term (PT).

The following imputation rules will be used for missing or incomplete AE start dates:

- Missing AE start day:
  - If the partial date contains a different month from the date of first study dose, then impute it as the first day of the month.
  - If it contains the same month as the date of first dose, then impute it as date of first dose.
- Missing AE start day and month:

- If the partial date contains a different year from the date of first dose, then impute the missing day and month as Dec 31.
- If it contains the same year as the date of first dose, then impute the missing day and month as day and month of first dose.
- Completely missing AE date:
  - Impute the missing date as the date of first dose.

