7.1.5 General Reporting Requirements

All serious and non-serious adverse events must be documented in the source records and on the respective section of the CRF, regardless of severity or the assumption of a causal relationship. The documentation includes: dates of onset and resolution, severity, seriousness, study drug intervention, treatment and outcome, as well as the causal relationship between the event and

CONFIDENTIAL

the study drug in accordance with Section 7.1.4. This documentation is required for all AEs that occur:

- a. from the date of signing the informed consent, and
- b. until the off-study date or 90 days after the last administration of study drug, whichever is longer, or until a new treatment is initiated (See Section 3.1.10 for subjects who begin other anti-cancer treatment).

Immune Related Adverse Events (irAEs) will be collected from the time of informed consent through 90 days after the last dose of the last study treatment (regardless of initiation of another therapy).

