## **3.6 Prior and Concomitant Medications/Procedures**

Prior and concomitant medications will be coded using the World Health Organization (WHO) Drug dictionary (Version Dec 2014).

A concomitant medication is defined as any drug or substance administered between the time of the first dose of study treatment and the time of the last study visit. This includes medications that were started prior to screening, if their use continued during or after dosing. In order to define whether a medication with missing start or stop dates is a concomitant medication, refer to the following additional criteria.

- if both the start and stop dates of a particular medication are missing, that medication will be considered concomitant;
- if the start date of a medication is missing and the stop date of that medication falls on or after the first dose date, that medication will be considered concomitant;
- if the start date of a medication is missing and the stop date of the medication is prior to the first dose date, that medication is considered *not* concomitant;
- If the start date of a medication is prior to the first dose date and the stop date of the medication is missing, that medication is considered concomitant.

Concomitant medication use will be classified by Anatomical Therapeutic Class (ATC) level 4 and PT for the ITT population. For the presentation of concomitant medications, the ATC level 4 terms will be sorted alphabetically, and within ATC level 4 term, the PT will be used and presented by decreasing total frequency overall.

Frequencies and percentages of subjects using each concomitant medication will be presented for the ITT population. Prior and concomitant medications and concomitant procedures/surgeries will be presented in subject listings.

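### The adverse-event start-date imputation in SAP 3.9.1 ignores the recorded stop date, so a screening event that ended before treatment can be dated to first dose and may be counted as treatment-emergent

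*SAP*

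**What the plan says.** SAP 3.9.1 gives five rules for incomplete adverse-event start dates.

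- **Day missing, month differs from first dose:** "If the partial date contains a different month from the date of first study dose, then impute it as the first day of the month".
- **Day missing, same month:** "If it contains the same month as the date of first dose, then impute it as date of first dose".
- **Day and month missing, year differs:** "If the partial date contains a different year from the date of first dose, then impute the missing day and month as Dec 31".
- **Day and month missing, same year:** "impute the missing day and month as day and month of first dose".
- **Start date fully missing:** the first-dose date is used.

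None of these mentions the stop date. SAP 3.1.4 says missing data are not imputed unless this is stated explicitly, so no unwritten check can be assumed.

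SAP 3.3.2 defines a treatment-emergent event (TEAE) as one first identified, or found to worsen, "at a time point occurring after the first dose of study drug". Protocol 4.2.2 likewise refers to events that begin or worsen after dosing. Neither says how an onset on the first-dose date is classified.

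Protocol 7.1.5 requires events to be documented "from the date of signing the informed consent", with both onset and resolution dates. The flowchart in Protocol 3.2 places screening at Day -28 to Day -1 and collects adverse events there.

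For concomitant medications the SAP does use the stop date. SAP 3.6 provides that "if the start date of a medication is missing and the stop date of the medication is prior to the first dose date", the medication is not concomitant.

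**The concern.** Dating an uncertain onset to first dose is a common cautious choice, because it keeps a doubtful event among the treatment-emergent ones. The caution has no basis when a recorded stop date shows that the event ended before treatment began. The rules have no exception for that case. They give such an event an onset later than its own end, on the date from which treatment emergence is judged.

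What is at stake is the accuracy of the TEAE tables, overall and by cohort (SAP 3.9.1.1 to 3.9.1.3). A pre-treatment event could be shown as arising on treatment while the data that disprove it sit in the same record. The SAP already applies the right logic to concomitant medications, so leaving it out for adverse events looks like an oversight.

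**Working it through.** The documents give no figure for this point, so there is none to reproduce. The check applies the rules as written to constructed records. All dates below are assumptions for illustration.

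**1. Screening events that ended before treatment (first dose 20 March 2016)**

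| Recorded start | Stop date | Rule | Imputed start | Days after resolution |
|---|---|---|---|---|
| March 2016 | 10 March 2016 | same month | 20 March 2016 | 20 − 10 = 10 |
| 2016 | 2 March 2016 | same year | 20 March 2016 | 20 − 2 = 18 |
| missing | 4 March 2016 | fully missing | 20 March 2016 | 20 − 4 = 16 |

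All three onsets fall on the first-dose date, and all three events had already ended. If that date counts as treatment-emergent, each is a false TEAE. If *after* first dose is read strictly, none is. A strict reading would also exclude genuine post-dose events that the rules moved to that date, which would defeat the purpose of the imputation. Onset after resolution is wrong on either reading.

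**2. The 31 December rule**

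- *Later year.* First dose 20 March 2016, start recorded as 2017, stop 9 January 2017. The imputed start is 31 December 2017, which is 356 days after resolution. The event is treatment-emergent before and after imputation.
- *Earlier year.* First dose 15 January 2016, start recorded as 2015, stop 24 December 2015. The imputed start is 31 December 2015, 7 days after resolution but still before treatment, so no false TEAE arises.

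**3. Rule that cannot fail this way**

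The first-of-month rule gives the earliest day of the known month, so it cannot place onset after the stop date.

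**4. How easily the same-month and same-year rules reach screening events**

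Assume first-dose dates spread evenly over a 365-day year, and count the 28 days before each: 365 × 28 = 10,220 screening days.

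- Same calendar month as first dose: 5,348 / 10,220 = 52%.
- Same calendar year: 9,814 / 10,220 = 96%.
- Collection starts at consent, not always on Day -28. If consent is instead spread evenly over Day -28 to Day -1, the same-month share becomes 67%.

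These are shares of screening days. They show that the rules can readily apply to screening events, but not how many events have incomplete dates.

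**5. Effect of one false TEAE on a table**

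SAP 3.9.1.2 counts a preferred term once per subject. The numerator rises by one only if the subject has no on-treatment event with that term. The percentage depends on the denominator: 1/6 = 16.7 points in a cohort of six (the size assumed for level 0a in Protocol 6.4), and 1/53 = 1.9 points if 53 subjects are taken as the total. The figure of 53 is the upper end of the anticipated evaluable number (Protocol 3.1.5), not the intent-to-treat denominator.

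**6. The remedy on the same records**

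With the start capped at the stop date and 1 January used for a later year, the three records in step 1 become 10, 2 and 4 March 2016, all before first dose. The 2017 record becomes 1 January 2017 and stays treatment-emergent. With the same cap, the 2015 record cannot start later than 24 December 2015 and stays pre-treatment. None then has an onset after its stop date.

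**The case against.** **The rule is conservative.** Where the stop date is missing, or falls on or after first dose, this stands and the rule should stay. It does not cover an event whose stop date is known to precede first dose.

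**An event dated to first dose may not be a TEAE at all.** Both definitions say after dosing, and SAP 3.3.2 turns on when the event was identified, so an event noted and resolved in screening would not qualify on a literal reading. This stands as a condition: the false TEAE depends on a same-day convention that the documents do not state. The impossible order of onset and resolution does not depend on it.

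**The triggering record is rare.** It needs a screening event with a known stop date before first dose and an incomplete start date. Protocol 7.1.5 requires both dates, and Protocol 7.2.2 and 7.2.4 provide for queries and source verification. This stands.

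**Shifts of up to a year look alarming but change no planned result.** This also stands. A reader might infer from the 31 December rule that reported results are distorted. SAP 3.9.1.1 to 3.9.1.7 plan incidence summaries and listings, with no time-to-onset or duration analysis, and neither document says that listings will print imputed dates.

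**The same-month wording.** A reader might also infer that the rule matches the month alone, so that an onset in March 2017 goes back to a first dose on 20 March 2016 (355 days if the true onset was 10 March 2017). When only the day is missing, the partial date contains month and year, and the ordinary meaning is that one calendar month. Onset then moves by at most 30 days. This is a point of wording, not a demonstrated failure.

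**Conclusion.** The concern holds in a limited form. The adverse-event start-date rules make no use of the stop date. A screening event known to have ended before treatment is dated to first dose when its start is fully missing or known only to the same month or year. It then enters the TEAE tables wrongly if onset on that date counts as treatment-emergent. The 31 December rule can also place onset after resolution, with no effect on TEAE status or on any planned adverse-event summary.

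The effect cannot be quantified, because the documents do not say how many start dates are incomplete. It is probably very small. A reader might infer that each such record adds 1.9 points to its preferred term, but that fails where the subject already has the term on treatment and in every by-cohort table. Nor is TEAE incidence the trial's safety endpoint. It is one of several safety variables in SAP 3.3.2, and the Phase 1 primary endpoint in Protocol 4 is DLT and MTD. The primary efficacy test is not affected. This is a low-priority correction, worth making because a stated rule gives a result that the recorded data contradict.

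**What to change.** Add to SAP 3.9.1:

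> *An AE with a known stop date before first dose is not treatment-emergent. An imputed start date may not be later than the stop date. An AE with start date imputed to the first-dose date, and stop date missing or on/after first dose, is treated as treatment-emergent.*

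The third sentence settles the same-day question and keeps the cautious treatment of doubtful events.

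For a start year later than the year of first dose, impute 1 January in place of 31 December. As a clarification of wording only, replace *same month* with *same month and year*.

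The cost is a few lines in the SAP and in the adverse-event derivation program. The stop date is already collected, so no new data are needed.
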